11.3.4. Efficacy

RCLASI

- Modified RCLASI Activity score will be derived by adding together patient's score for Erythema, Scaling/Hyperkeratosis (group B only) and Edema/infiltration. If any one of these components are missing, then the modified RCLASI Activity Score will be set to missing.

Modified RCLASI Activity score = Erythema + Scaling/Hyperkeratosis (group B only) + Edema/Infiltration

- Overall Modified RCLASI score will be derived by summing the activity and dyspigmentation score. If any one of these components is missing, then the overall modified RCLASI Score will be set to missing.

- Overall Modified RCLASI Score = Modified RCLASI Activity score + Dyspigmentation

11.3.5. Biomarker

IFN mRNA signature																																																											

 Genes to be reported in the descriptive and analysis summary include, but not limited to: 
 CXCL10 IFI16 IFI44 IFI44L IFIH1 MX1 MX2 OAS1 OAS2 OAS3 IFIT1 IFIT3 OASL ISG15 IL1A IL1B IL6 
Since each gene has multiple probesets, the following table highlights the probesets which have, historically, been of good quality and hence will be used for the analysis in this study. Entrez ID is also specified, which is a unique code a gene. These can be used at the programming stage to subset from multiple genes and probesets.
 
  
 PROBESID	GENESYMB	Entrez_ID	
   
204533_at	CXCL10	3627	
 
206332_s_at	IFI16	3428	
 
208965_s_at	IFI16	3428	
 
208966_x_at	IFI16	3428	
 
214059_at	IFI44	10561	
 
214453_s_at	IFI44	10561	
 
204439_at	IFI44L	10964	
 
1555464_at	IFIH1	64135	
 
216020_at	IFIH1	64135	
 
219209_at	IFIH1	64135	
 
203153_at	IFIT1	3434	
 
204747_at	IFIT3	3437	
 
229450_at	IFIT3	3437	
 
208200_at	IL1A	3552	
 
210118_s_at	IL1A	3552	
 
205067_at	IL1B	3553	
 
39402_at	IL1B	3553	
 
205207_at	IL6	3569	
  
			PROBESID	GENESYMB	Entrez_ID	204533_at	CXCL10	3627	206332_s_at	IFI16	3428	208965_s_at	IFI16	3428	208966_x_at	IFI16	3428	214059_at	IFI44	10561	214453_s_at	IFI44	10561	204439_at	IFI44L	10964	1555464_at	IFIH1	64135	216020_at	IFIH1	64135	219209_at	IFIH1	64135	203153_at	IFIT1	3434	204747_at	IFIT3	3437	229450_at	IFIT3	3437	208200_at	IL1A	3552	210118_s_at	IL1A	3552	205067_at	IL1B	3553	39402_at	IL1B	3553	205207_at	IL6	3569
PROBESID	GENESYMB	Entrez_ID																																																									
204533_at	CXCL10	3627																																																									
206332_s_at	IFI16	3428																																																									
208965_s_at	IFI16	3428																																																									
208966_x_at	IFI16	3428																																																									
214059_at	IFI44	10561																																																									
214453_s_at	IFI44	10561																																																									
204439_at	IFI44L	10964																																																									
1555464_at	IFIH1	64135																																																									
216020_at	IFIH1	64135																																																									
219209_at	IFIH1	64135																																																									
203153_at	IFIT1	3434																																																									
204747_at	IFIT3	3437																																																									
229450_at	IFIT3	3437																																																									
208200_at	IL1A	3552																																																									
210118_s_at	IL1A	3552																																																									
205067_at	IL1B	3553																																																									
39402_at	IL1B	3553																																																									
205207_at	IL6	3569																																																									

205483_s_at	ISG15	9636
202086_at	MX1	4599
204994_at	MX2	4600
202869_at	OAS1	4938
205552_s_at	OAS1	4938
204972_at	OAS2	4939
206553_at	OAS2	4939
228607_at	OAS2	4939
218400_at	OAS3	4940
232666_at	OAS3	4940
205660_at	OASL	8638
210797_s_at	OASL	8638

Immunohistochemistry (IHC) biomarkers

Cells in lesional biopsies are measured by IHC. Single stains include but are not limited to; pSyk+, tSyk+, MxA+, CD3+, CD20+, CD68+, CD11c+, CD123+, Dual stains include but are not limited to; pSyk/tSyk, pSyk/CD11c, pSyk/CD123, in Epidermal, Dermal and combined areas of skin.

Each single/dual stain is assessed at 20x magnification across the whole 1 layer (3.5um slice) of the biopsy by automated image analysis and normalised by area (mm²). The regions of interest are the epidermis, dermis and glass, however only cells within the epidermis and dermis are analysed, which are classified by the automated image analysis software HALO. A manual QC process will be conducted on the software assigned regions of interest if necessary at the discretion of the operator, including but not limited to removal or addition of incorrectly classified areas within HALO. Other artefacts (tissue folding, stain precipitation) will be excluded from the ROI manually at the discretion of the operator and confirmation by the pathologist.

The number of positive cells for each marker will be calculated from the single or dual stain where appropriate. The reportables will include but are not limited to the total number of cells for each marker normalised by area (mm²), total area (mm²), total number of cells per mm², percentage of dual positive cells from total cells and percentage of each marker that is positive for both markers in the dual stains where applicable. These values will be provided for both dermis and epidermis separately, and combined, and will be derived by the BIB group within GSK prior to data transfer.

Histopathology score

- The component scores (patient's parakeratosis, ballooning\hydropic degeneration, epidermal cell-death, junctional inflammation and dermal inflammation scores) are scored twice by two independent investigators. Derivation,

$$\text{Mean component score} = (\text{score 1} + \text{score 2})/2$$

will be used to derive the mean component scores for each patient. This will be used for the

descriptive summaries. If one of the scores missing then the other score will be used as the mean component score.

- Overall histopathology score will be derived by summing derived mean component scores for patient's parakeratosis, ballooning\hydropic degeneration, epidermal cell-death, junctional inflammation and dermal inflammation scores. This will be used for the descriptive summaries.
- Note for listing only: For each score, the overall histopathology score will be derived by summing component scores for patient's parakeratosis, ballooning\hydropic degeneration, epidermal cell-death, junctional inflammation and dermal inflammation scores. This will be used for the descriptive summaries.

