## **7.6. Biomarker(s)/Pharmacodynamic Markers**

### **7.6.1. Biomarker(s)/Pharmacodynamic measurements in Skin Biopsies**

For group A, two pre-dose biomarker / PD biopsies will be obtained at day 1, one from an uninvolved skin region on the back of the patient (skin area E), and one from PV lesion B. At day 28, post-treatment biomarker / PD biopsies will be obtained from the two remaining non-biopsied PV lesions A and C, one PV lesion treated with study drug and one PV lesion treated with placebo.

For group B, three pre-dose biomarker / PD biopsies will be obtained at day -5 to -3, one from an uninvolved skin region (H) and from both of the existing lesions F and G. Ideally, the uninvolved skin region biopsy should be located on the same anatomical body area close to the existing lesion biopsy. At day 28, post-treatment biomarker / PD biopsies will be obtained from both of the existing lesions F and G, one existing lesion treated with study drug and one lesion treated with placebo.

Details of biomarker / PD skin biopsy sample processing, storage and shipping procedures are provided in the Study Reference Manual (SRM).

Biomarker / PD biopsies will be evaluated histologically and by transcriptomic analysis.

Transcriptomic analysis will determine the effect of placebo and active treatment on IFN gene expression. Gene expression will be measured using microarray technology, and/or

alternative equivalent technologies, which facilitates the simultaneous measurement of the relative abundances of thousands of RNA species resulting in a transcriptome profile for a skin biopsy sample. Genes may include but are not restricted to: MX1, MX2, OAS1, OAS2, IFI44. The same samples may also be used to confirm findings by application of alternative technologies.

Histological assessments of the biopsies will explore changes in pharmacodynamic and disease biomarkers. Markers may include (but are not restricted to):

IFN proteins (such as MxA) to assess changes in IFN signalling

SYK protein levels (such as but not restricted to phospho-SYK and total SYK) to assess target engagement

Immune cell and immune cell marker expression (such as CD3+ T cells, CD20+ B cells, CD11c+ myeloid dendritic cells and CD68+ macrophages).

Pathological evaluation for general appearance using a histopathological disease activity score, scoring on parakeratosis, ballooning, necrosis, junctional inflammation and the extent of dermal infiltrate.

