#### **9.4.2. Secondary Analyses**

All plasma GSK2646264 concentration data will be graphically represented, descriptively summarised and listed appropriately. Plasma GSK2646264 concentration time data will be analysed using a population pharmacokinetics (PK) model developed previously using data from study 200196 (FTIH of GSK2646264). Population PK parameters (Cmax, AUC(0- $\tau$ ) and terminal phase half life (t1/2) will be reported. Pharmacokinetic data will be presented in graphical and/or tabular form and will be summarized descriptively. All pharmacokinetic data will be stored in the Archives, GlaxoSmithKline Pharmaceuticals, R&D.

Descriptive statistics of both raw and change from baseline, where appropriate, (i.e. n, arithmetic mean, standard deviation, minimum, median and maximum) will be calculated

for erythema, oedema, dyspigmentation (and scaling in existing lesions only) and modified RCLASI and summarized study part. All data will be listed.

Change from baseline in each clinical activity assessment will be analysed for each lesion type using a mixed effects model fitting visit, treatment and lesion location as fixed effects and subject as random. Estimates of the differences between GSK2646264 and placebo will be calculated and appropriate statistical inferences based on these results will be made.

Descriptive statistics of both raw and change from baseline data, where appropriate, (i.e. n, arithmetic mean, standard deviation, minimum, median and maximum) will be calculated for the IFN mRNA endpoints and summarized by lesion type (PV and natural lesions). All data will be listed.

If data permits, formal statistical analyses of the IFN mRNA endpoints may be conducted.

Change from baseline in each IFN mRNA signature endpoints will be analyzed by study part using a mixed model including treatment and lesion number as fixed effects and subject as a random effect. Estimates of the treatment means and differences will be presented with the associated 95% confidence intervals. Distributional assumptions underlying the analyses will be assessed as appropriate. If these assumptions are strongly violated, appropriate transformations will be investigated and if required alternative statistical analyses considered.

Full details will be provided in the RAP.

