2.2. Study Objective(s) and Endpoint(s)

[figure not shown]
Objectives	Endpoints
Primary Objectives	Primary Endpoints

 • To evaluate the safety and tolerability of repeat doses of a cream formulation of GSK2646264 in patients with CLE 	
 • Safety and tolerability by laboratory tests, vital signs, 12-lead ECG, and AE reporting.
Secondary Objectives	Secondary Endpoints

 • To determine the effect of GSK2646264 on the reduction in clinical activity score from baseline in treated PV and existing CLE lesions • To evaluate the plasma concentrations of GSK2646264 in patients with CLE • To determine the effect of GSK2646264 on expression of IFN mRNA signature in skin biopsies in treated PV and existing CLE 	
 • Change from baseline of components of a modified RCLASI- composite clinical activity score at day 14 and day 28 in PV and existing lesions in erythema, oedema, dyspigmentation and (scaling in existing CLE lesions only) • PK parameters, including but not limited to AUC, Cmax, tmax, half-life ($t_{1/2}$) if data permits. • Change from baseline in IFN mRNA signature in skin biopsies at day 28 in PV and existing CLE lesions

Objectives	Endpoints
lesions	
Exploratory Objectives	Exploratory Endpoints

 To determine the effect of GSK2646264 on expression of IFN protein markers in skin biopsies in treated PV and existing CLE lesions 	
 Change from baseline in IFN proteins (e.g. MxA, CXCL10) in skin biopsies at day 28 in PV and existing CLE lesions

 To determine the effect of GSK2646264 on expression of pSYK and SYK protein in skin biopsies in treated PV and existing CLE lesions 	
 Change from baseline in pSYK and SYK protein in skin biopsies at day 28 in PV and existing CLE lesions

 To determine the effect of GSK2646264 on immune cell markers in skin biopsies in treated PV and existing CLE lesions 	
 Change from baseline in immune cell proteins (e.g. CD3, CD20, CD11c, CD123, CD68) in skin biopsies at day 28 in PV and existing CLE lesions

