8.3.2. Planned Pharmacodynamic and Biomarker Statistical Analyses

Planned Statistical Analyses
Endpoint(s)

 • IFN mRNA signatures
Model Specification
Microarray mRNA data have been collected from the skin biopsy in both GSK2646264 and placebo

Planned Statistical Analyses

treated lesions on Day -5 to -3 (Baseline) and Day 28.

To compare the expression value for each probe set, the following mixed- effects model will be fitted to each probe set, with mRNA intensity (\log_2 scale) as the response variable.

Baseline is defined as the measurement taken pre-dose at baseline of each treated lesions (i.e lesion-specific baseline).

The baseline observation will be defined as an additional response measured on the same subject prior to application of the treatment. Then this observation is not affected by any of the effects included in the basic model for the response.

Visit	Trt	XTrt
Baseline	GSK2646264	NA
Baseline	Placebo	NA
Day 28	GSK2646264	GSK2646264
Day 28	Placebo	Placebo

The model will include:

- Fixed terms: Treatment (Xtrt: Placebo, GSK2646264, NA), Visit, Visit and Treatment (Xtrt) interaction
- Random: Subject (in sas Random intercept /subject=subjid)
- Repeated: Visit (in SAS Repeated visit / subject=subjid type=un)

For each probe set analysed adjusted means with corresponding 95% CI and fold changes with corresponding 95% CI's will be outputted. The fold change is derived from the ratio of the back-transformed estimate of the difference (GSK2646264 – Placebo) between adjusted means.

Since the data will be \log_2 transformed prior to the analysis the treatment effects will be expressed as ratios after back transformation. These ratios can be converted from treatment ratios to fold change values as follows:

- If ratio ≥ 1 then fold change = ratio
- If ratio < 1 then fold change = $-1/ratio$

Model Checking

- Refer to [Appendix 6](#) : Model Checking and Diagnostics for Statistical Analyses.

Model Results Presentation

- Back transformed baseline-adjusted means along with 95% CIs will be calculated for each treatment group. Additionally, fold changes between active and placebo in change from

Planned Statistical Analyses
baseline intensity will be calculated, along with 95% CI.
Endpoint(s)

 IFN mRNA signatures
Model Specification

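### The IFN mRNA signature endpoint is reported only as 30 separate probe-set intervals; one pre-specified signature score would be a cheap improvement

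*SAP*

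**What the plan says.** Protocol section 3 and SAP 2.2 state the endpoint in the singular: "Change from baseline in IFN mRNA signature in skin biopsies at day 28 in PV and existing CLE lesions". Protocol 9.4.2 uses a plural: "Change from baseline in each IFN mRNA signature endpoints will be analyzed by study part using a mixed model". Protocol 7.6.1 names five genes and leaves the list open: "Genes may include but are not restricted to: MX1, MX2, OAS1, OAS2, IFI44".

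SAP 11.3.5, under the heading for the signature, lists 17 genes, introduced by "Genes to be reported in the descriptive and analysis summary include, but not limited to". The list ends with "OASL ISG15 IL1A IL1B IL6". The probe sets are then selected: "Since each gene has multiple probesets, the following table highlights the probesets which have, historically, been of good quality and hence will be used" in the analysis.

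SAP 8.3.2 sets the unit of analysis: "the following mixed- effects model will be fitted to each probe set". The output follows the same unit: "For each probe set analysed adjusted means with corresponding 95% CI and fold changes", also with 95% CIs. The SAP gives no score, weighting, gene-level summary, lead gene, multiplicity adjustment or rule for reading the results together. The display list in SAP 11.8.10 and 11.8.11 contains no signature-level table or figure.

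**The concern.** The objective asks what the drug does to the IFN signature. The planned output answers 30 narrower questions and leaves the reader to combine them. With no lead result, emphasis can settle on whichever probe sets look favourable.

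Two features add to this. First, SAP 2.1 and 8.1.2 drop formal analysis of the clinical score, so the mRNA model is the only secondary endpoint in SAP section 8 that keeps a modelled active-placebo comparison. Second, the sponsor is unblinded and Protocol 9.3.2 allows unblinded reviews during the study, so a gene list with an open end could be extended by people who have seen results.

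The SAP does build totals elsewhere: modified RCLASI (11.3.4), histopathology (11.3.5) and skin irritation (11.3.3). It has no equivalent step for the endpoint that is named as a signature.

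**Working it through.** There is no figure in the plan to reproduce. Protocol 9.2 and 9.2.1 give no power or sample size calculation for this endpoint. The gene-level precision table in the Amendment 3 change log is superseded text and was not used.

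**Count from the table in SAP 11.3.5**
- One probe set: CXCL10, IFI44L, IFIT1, IL6, ISG15, MX1, MX2 (7 genes, 7 probe sets).
- Two probe sets: IFI44, IFIT3, IL1A, IL1B, OAS1, OAS3, OASL (7 genes, 14 probe sets).
- Three probe sets: IFI16, IFIH1, OAS2 (3 genes, 9 probe sets).
- Total: 7 + 14 + 9 = 30 probe sets over 17 genes.
- IL1A, IL1B and IL6 account for 2 + 2 + 1 = 5 probe sets. Without them, 25 probe sets over 14 genes remain.

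The active-placebo contrast therefore gives 30 intervals. The skin-type model in SAP 8.3.2 adds four fold changes per probe set, 4 x 30 = 120 more; these are not counted below.

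**False exclusions if the drug has no effect**
- Expected number of 95% CIs excluding no effect: 30 x 0.05 = 1.5, whatever the correlation.
- Chance of at least one, if independent: 1 - 0.95^30 = 0.785.
- Chance of at least one, if correlated: simulated with 30 equally correlated paired differences, n = 15 (the planned group B size), t intervals and 20,000 replicates. The correlations are assumed.

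| Assumed correlation | At least one of 30 | One composite score |
|---|---|---|
| 0 | 79% | 4.9% |
| 0.3 | 68% | 5.1% |
| 0.5 | 53% | 5.0% |
| 0.7 | 37% | 5.2% |
| 0.9 | 18% | 5.0% |

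**Precision of a 14-gene mean relative to one gene**

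With equal variances and common correlation r, the SD ratio is sqrt(r + (1 - r)/14).
- r = 0.3: sqrt(0.350) = 0.59, so about 41% narrower.
- r = 0.5: sqrt(0.536) = 0.73, about 27% narrower.
- r = 0.7: sqrt(0.721) = 0.85, about 15% narrower.
- r = 0.9: sqrt(0.907) = 0.95, about 5% narrower.

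**Gene content, documents side by side**

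All five genes named in Protocol 7.6.1 are in the SAP list. IL1A, IL1B and IL6 are in the SAP list, but the protocol does not name them as IFN genes. CXCL9 and IRF1, named in Protocol 2.1 in connection with interferon, are not in the SAP list. In SAP 11.8.10 the mRNA table titles refer to inflammatory transcripts, while in 11.8.11 the figure titles refer to IFN signatures.

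**The case against.** The strongest reply is that the signature was always a set of genes to be reported one by one. Protocol 9.4.2 and the SAP synopsis speak of each signature endpoint, and SAP 8.3.2 and 11.6.1 use the plural. This stands: per-gene reporting has a basis, and neither document promises a single score. What neither does is say how the members are to be read together.

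Three stronger readings are tempting and are not supported.

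- **A reader might infer an inflated type I error.** Protocol 9.1 and SAP 2.4 call these comparisons exploratory, and the plan sets no alpha or success rule for them, so nothing is breached. The 79% is also an upper figure. In the table, 23 of 30 probe sets share a gene with another listed probe set, and Protocol 2.1 describes co-expression with IFN-stimulated genes, so independence is implausible.
- **A reader might infer that the analysis set itself is open.** The open wording attaches to the gene bullets. The probe-set table is fixed for the analysis, and Tables 5.2 and 5.3 point to 11.3.5 for what is analysed. The two statements need reconciling, no more.
- **A reader might infer that the interleukins are wrongly included.** No passage says that they lie outside the signature, and the protocol's list is expressly non-exhaustive. The documents support asking for a justification, not removal.

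It is also fair that the benefits shrink as correlation rises. At r = 0.9 the gain in precision is about 5%, and averaging helps only if the effect is broadly similar across genes. The case for a score then rests mainly on having one stated answer.

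**Conclusion.** The point holds as a low-cost improvement, not as an error in the plan. A secondary endpoint named as a signature is delivered as 30 unranked, unadjusted intervals with no summary, which leaves it open to selective reading.

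The count of 30 and the expected 1.5 false exclusions follow directly from the SAP. The chance of at least one false exclusion, anywhere from 18% to 79%, depends on a correlation that the documents do not give. The precision gain of 5% to 41% rests on assumed correlations and equal variances. It also takes the 14 genes left after setting aside the three interleukins as an illustration, since the documents do not classify most of the listed genes.

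**What to change.** In SAP 11.3.5, define one score per biopsy: average log2 intensity over probe sets within each gene, then average over a closed list of IFN genes taken from the existing table. Averaging within gene first stops genes with three probe sets from outweighing those with one. In 8.3.2, analyse the score with the planned GSK2646264-placebo contrast, present it first for this endpoint, and keep the probe-set tables and figures as supportive.

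Delete the open-ended qualifier in the lead-in to the gene list, or state that any added gene will be labelled post hoc. Because the sponsor is unblinded, the useful deadline is before expression data are analysed by treatment, not formal unblinding. State why IL1A, IL1B and IL6 belong to the IFN signature, or report them separately, and use one name for the endpoint in table and figure titles.

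The cost is one derived variable, one more model and a small addition to the displays. The drawback is that a composite can mask an effect confined to one gene; the retained probe-set tables would still show it.

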11.4. Appendix 4: Premature Withdrawals & Handling of Missing Data

11.4.1. Premature Withdrawals

Element	Reporting Detail
General	
 Subject study completion (i.e. as specified in the protocol) was defined as subject who receives at least 25 days of study drug and completes the end of treatment biopsy and assessment. Withdrawn subjects may be replaced in the study. All available data from subjects who were withdrawn from the study will be listed and all available planned data will be included in summary tables and figures, unless otherwise specified.

